7.5 Qualitative assessments

Phase 2: HCPs

Qualitative interviews:

A sub-set of HCPs (purposively selected for diversity) will be invited to take part in post-READY semi-structured research interviews to understand their experiences of the programme, how they have understood the core concepts and their expectations around supporting PwMS to use the programme. These interviews will also seek to understand how, when, and in what contexts different HCPs might ask their patients about employment and difficulties at work.

Phase 3: PwMS

Qualitative interviews:

A sub-set of PwMS (purposively selected for diversity) will be invited to complete post-intervention and 6-month follow-up semi-structured interviews to explore their experience of the programme and any long-term impact.

7.6 Lightning Reports

At Phase 3, all research participants ≥2 weeks from baseline (HCPs and PwMS) will receive an email-based pulse free-text questionnaire at 2-weekly intervals to ask:

- 1. What has been going well with the READY programme
- 2. What has not been going well with the READY programme
- 3. Any recommendations for improvement to the READY programme

Participants will also be invited to take part in optional additional unstructured tele-interviews to discuss their responses further. During these tele-interviews, the researcher will invite participants to expand on their responses given to the 3 key questions details above. Participants will be asked for verbal consent to audio-record these tele-interviews.

Responses to the pulse questionnaires will be assessed by rapid qualitative analysis to contribute to lightning reports (see Brown-Johnson et al., 2019³⁹).

8 STATISTICS AND DATA ANALYSIS

8.1 Sample size calculation

A minimum of 200 cases is recommended for Structural Equation Modelling (SEM) frameworks⁴⁰. Assuming an attrition rate of 20%⁴¹, recruitment rate of at least 250 subjects should provide this minimum recommended number of cases.

The minimal clinical important difference for the MS-WIS is yet to be established. The MS-WIS has been shown to be predictive of job loss over a 28 month period, following up a cohort of those in work at the onset³⁸.

8.2 Statistical analysis plan

This is a hybrid trial assessing implementation and effectiveness of the digital READY programme in NHS settings.

In terms of effectiveness, this study seeks to understand who might benefit from the digital READY intervention and in what contexts. Participant outcomes (e.g. Work Instability, Psychological flexibility, Self-efficacy) will be measured at multiple time-points (baseline, week 8 and month 6). While the first step will be to assess for any change to outcome variables over time using repeated measures ANOVA, this provides only an overview of interventional impact and assumes homogenous change within the study group⁴². Latent Growth Curve Modelling (LGCM) can be useful to identify patterns within subgroups of a population to understand who benefits from an intervention and why⁴³. Latent Growth Curve Modelling (LGCM) will be used to determine trajectories over time. Changes from baseline to week 8 and baseline to month 6 will be assessed. Logistic regression models will be utilised to understand potential predictors of these trajectories. Specifically, the relationship between psychological flexibility, resilience, and work instability, how these change for participants from baseline to post-intervention and longer term, and if changes in these variables seem to be linked. If there is evidence of a relationship between work instability and resilience or psychological flexibility over time, such that increases in resilience or psychological flexibility relate to decreases in work instability, this would suggest that the READY programme could be effective in reducing work instability.

Lightning reports will be produced using rapid qualitative synthesis following a pre-defined framework³⁹. These lightning reports will enable iterative assessments of implementation that will inform the final qualitative assessments.

The process evaluation will help to identify contextual factors that may influence core processes of the intervention through qualitative inquiry.

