It is important to test whether the READY intervention can be plausibly implemented in an NHS or community healthcare setting. If there are barriers to using this intervention in this setting, there is unlikely to be significant uptake and therefore the intervention cannot reliably benefit PwMS. Assessing the effectiveness of integrating an intervention option that can be supported by healthcare professionals in a way that reduces rather than increases long-term burden is also important. Giovannetti et al³⁷ found that where health professionals were supported to undertake and deliver a group-based READY programme, beneficial outcomes included resilience, ACT skills development, and reduced vulnerability to burnout.

The integrated process evaluation allows us to assess in-depth what will work and what might need to be adjusted prior to investing time and resources to a large-scale randomised control trial (RCT). While this study will focus primarily on the impact of risk of job loss for PwMS, previous versions of the READY programme have been shown to improve a range of

psychological factors that influence quality of life in MS³⁴. Therefore, successful implementation of this programme by healthcare professionals could lead to wider use of this programme for PwMS in a range of settings who may benefit from resilience-training interventions.

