will also seek to understand how, when, and in what contexts different HCPs might ask their patients about employment and difficulties at work. The week 3 support calls will be audio-recorded by the psychologist. Anonymised troubleshooting examples that arise from the Week 3 HCP-psychologist support calls will be utilised to develop 'case examples' in a 'troubleshooting toolkit'. This troubleshooting toolkit will be shared with PwMS who use the programme and a copy given to HCPs to aid support conversations.

Phase 3: PwMS

The CI and local PIs will work with HCPs to identify PwMS who are experiencing difficulties at work. The CI will also work to engage with different MS communities to invite PwMS to the study. PwMS will complete a screening MS-WIS (MS Work Instability Scale) and those with a score of 11 (medium WI) or above will be invited to enter the study. PwMS will complete a baseline digital questionnaire pack including MS-WIS, CD-RISC-10 (Connor-Davidson Resilience Scale), USE-MS (Unidimensional self-efficacy scale for MS) and MPFI (Psychological Flexibility) scales. Participants will be asked to consent to be contacted by a trained HCP who will offer support in completing the READY programme. PwMS will be provided with a link to the digital READY programme, the accompanying READY workbook and the troubleshooting toolkit. HCPs will conduct the interval support calls and record notes on any troubleshooting that arises from these support conversations. PwMS will be invited to complete a follow up digital questionnaire pack on completion of the READY programme, to measure post-intervention work instability, self-efficacy and psychological flexibility. PwMS will be invited to complete this questionnaire pack again at a further follow up time-point of 6 months. A small subset of PwMS will be invited to complete post-intervention and 6-month follow-up semi-structured interviews to explore their experience of the programme and any long-term impact.

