11.3 Public and Patient Involvement

Design: PwMS were involved in the co-development of the MS-Work Instability Scale. This is the primary outcome measure in the MS-PROACTIVE trial.

The 'READY for MS' Acceptance and Commitment Therapy programme was developed by [name] in Australia to improve resilience and self-efficacy. The programme has been tested by PwMS in Australia and in Italy.

The pilot study that precedes this proposal was submitted to the MS Society Research Network for lay review and received positive comments on the importance of research on employment and MS, as well as support for testing of an online intervention.

PwMS were involved in the development and design of the READY digital programme as part of a co-production phase for the current pilot study. Therefore the digital programme that we would now like to trial in an NHS setting has been developed by and for PwMS.

Two occupational therapists provided written feedback at the design stage of this research project. Based on this feedback, we will provide the HCP training sessions in groups virtually to encourage peer support

We submitted this research proposal to the MS society research network and received 4 lay review and 3 peer review responses. PwMS felt positively about a psychological intervention for PwMS who are struggling to stay in work, as well as the potential wider benefits of the READY programme for psychological outcomes. PwMS were also in favour of resources being available online.

Focus groups will be utilised to explore priorities for PwMS and ensure our final study design is in line with these. We will actively recruit people from diverse backgrounds for the focus groups to identify how we might better engage with different communities before recruitment begins.

Management of the research: The Chief Executive of Shift.ms who has multiple sclerosis is an advisor for this project and a member of the Trial Management Group. The Trial Steering Committee will have representation from PwMS.

Participants will be invited to contribute to lightning reports which will inform the ongoing running of the study.

Undertaking the research: 50 HCPs and 250 PwMS will be invited to complete the READY programme. 5 HCPs and 10 PwMS will be invited to complete research interviews which will contribute toward the process evaluation. The embedded process evaluation will be an opportunity to explore qualitatively the contexts that act as barriers or facilitators to people

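### Section 8.2 presents predictors of trajectory as showing who might benefit from READY, but without a comparator they show only who changes during READY

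*Protocol*

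**What the plan says.** Section 8.2 (Statistical analysis plan) states the effectiveness question in these terms: "this study seeks to understand who might benefit from the digital READY intervention and in what contexts". It presents latent growth curve modelling as a way to learn which people gain from an intervention and why, and adds: "Logistic regression models will be utilised to understand potential predictors of these trajectories". It gives no list of baseline predictors and does not name baseline MS-WIS as one.

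There is one group of patients. Section 11.3 says "50 HCPs and 250 PwMS will be invited to complete the READY programme", and no control group is described. The Rationale (section 2) mentions a randomised trial only as a possible later step.

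Entry depends on the scale that is also a primary outcome. Under section 4, Phase 3, "PwMS will complete a screening MS-WIS (MS Work Instability Scale) and those with a score of 11 (medium WI) or above" are invited to enter. Table 3 schedules MS-WIS at screening (T-1) and again at baseline (T0). Sections 7.3 and 7.4 also collect likely prognostic variables: MS subtype and treatment status from medical records, and recent relapse by questionnaire.

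**The concern.** Benefit is the difference between a person's course with READY and the course that person would have had without it. The study observes only the first. Suppose people with one MS subtype, or without a recent relapse, show a better MS-WIS trajectory. They may respond more to READY, or they may simply be the people who do better anyway. The planned analysis gives the same answer in both cases, yet section 8.2 invites the reader to take it as the first.

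A narrower issue sits beside this. Baseline severity is an obvious candidate predictor, because the trial screens on it and section 2.1 argues that improvement is hard to measure when work instability is already low. If the observed T0 score is used to predict change measured from that same score, its measurement error enters both sides with opposite sign. High scorers then tend to look like improvers whatever READY does.

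At stake is the meaning of the subgroup answer, which is a stated purpose of the effectiveness analysis and would be available when a later randomised trial is designed.

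**Working it through.** **1. The plan's own figure.** Section 8.1 says "A minimum of 200 cases is recommended for Structural Equation Modelling (SEM) frameworks", assumes 20% attrition and concludes that a "recruitment rate of at least 250 subjects should provide this minimum recommended number of cases". Check: 200 / (1 - 0.20) = 250, and 250 x 0.80 = 200. The figure reproduces. The point does not affect it, and n = 200 is used below.

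**2. Why one arm cannot answer the question.** For people with characteristic x, let D1(x) be the mean change in MS-WIS with READY and D0(x) the mean change without it. Lower scores are better, so benefit is B(x) = D0(x) - D1(x), which gives

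D1(x) = D0(x) - B(x).

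Compare two groups, a and b:

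D1(a) - D1(b) = [D0(a) - D0(b)] - [B(a) - B(b)].

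The data estimate the left side only. The first bracket is prognosis and the second is effect modification. There is one equation and two unknowns. A growth model, latent classes or logistic regression changes how D1 is described and supplies no information on D0. This step needs no numerical assumption.

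**3. The conditional issue: observed baseline predicting its own change.** With no effect, equal variances and retest correlation rho, and before any selection,

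corr(baseline, change) = (rho - 1) / sqrt(2(1 - rho)) = -sqrt((1 - rho)/2).

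For rho = 0.7, 0.8 and 0.9 this is -0.39, -0.32 and -0.22.

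Selection at screening narrows the spread of true scores, so error becomes a larger share of what remains. A simulation with no effect shows this. All of the following are assumptions: true score normal with mean 11.5, total SD 5, scores rounded and held to 0-22, entry if screening is 11 or more, 400,000 draws per setting. The eligible share is 58%, against 37.0% + 20.2% = 57.2% in the reference cohort of section 7.1.1.

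| Reliability (assumed) | T0 vs change, independent errors | Screening score vs change, independent errors | T0 vs change, T-1/T0 error correlation 0.6 | Screening score vs change, T-1/T0 error correlation 0.6 |
|---|---|---|---|---|
| 0.7 | -0.47 | 0.00 | -0.37 | -0.15 |
| 0.8 | -0.41 | 0.00 | -0.31 | -0.12 |
| 0.9 | -0.32 | 0.00 | -0.23 | -0.08 |

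At n = 200, t = r x sqrt(198 / (1 - r^2)). For |r| = 0.32, t = 4.75 and p is about 4 in a million. For |r| = 0.23, t = 3.33 and p is about 0.001. The threshold for p < 0.05 is about 0.14.

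With independent errors, a fall of 3 points or more occurs by chance in 42%, 33% and 19% of the top baseline third (reliability 0.7, 0.8, 0.9), against 11%, 9% and 7% of the bottom third.

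**4. The same issue under the planned methods.** A second null simulation used 200 completers, 400 replicates per setting, normal scores cut at z = -0.18 (the point with 42.8% below it) and a T0 measured separately from screening. Stable-trait share of variance was 0.6 to 0.9. Errors were either independent or autocorrelated (0.6 per month).

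- Logistic regression for a fall of at least 0.5 SD by month 6: odds ratio per SD of T0 from 2.67 down to 1.75 with independent errors (significant in 100% down to 81% of replicates), and from 1.91 down to 1.39 with autocorrelated errors (98% down to 42%).
- Logistic regression for the steepest-falling third of observed slopes: odds ratios 1.33 to 2.20, significant in 49% to 100%.
- Latent intercept-slope covariance of a growth model: about zero (-0.0001 to 0.0001) with independent errors, and -0.0008 to -0.0046 with autocorrelated errors.

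The artefact therefore belongs to observed scores and slopes. It is largely absent from the latent intercept, provided T0 is a separate measurement. When the screening score itself served as T0, that covariance was distorted in the positive direction (0.0016 to 0.0278).

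**The case against.** The wording of section 8.2 is tentative throughout, and the study is placed before any large randomised trial. The part of the question about contexts is also addressed by the qualitative process evaluation. This is fair, but tentative wording does not help when no strength of association could answer the question. An unseen SAP could define trajectory classes and list covariates, but it could not supply a comparator.

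The objection has more force against three stronger readings that a reader might infer.

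- *Baseline MS-WIS is bound to appear as a strong predictor of benefit.* The protocol does not name it as a predictor. The text after the logistic regression sentence concerns links between changes in flexibility, resilience and work instability. The choice of covariates may properly be left to the SAP. No MS-WIS reliability is given, and with autocorrelated error and high reliability the null odds ratio is only 1.39, significant in 42% of replicates.
- *The baseline artefact persists however trajectories are modelled.* It does not: the latent intercept-slope covariance of the planned growth model is close to zero. That phrase holds only for the missing comparator.
- *The results will be used to select patients for READY.* The documents do not say so. It is a possible use, not a stated one.

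**Conclusion.** The aim in section 8.2 is wrong as written. With every participant offered READY, the planned analyses identify predictors of course and cannot separate prognostic factors from modifiers of READY's effect, whichever trajectory model is used. This conclusion rests only on the design in the protocol. It concerns the subgroup claim and leaves the recruitment target of 250 untouched.

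The caution about MS-WIS is conditional. It applies if severity is entered as the observed T0 score and the outcome is observed change or groups built from observed scores or slopes. The null correlation is then about -0.47 to -0.32 for reliability 0.7 to 0.9 with independent errors, and -0.37 to -0.23 with T-1/T0 error correlation 0.6. Reliability, error structure, normality, the SD and the cut-offs for improvement are all assumed, so these figures show a plausible range and do not predict this trial's result.

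**What to change.** In section 8.2, restate the question as: which characteristics are associated with change during READY. Bring the sentence on the purpose of growth curve modelling into line, and state that who benefits (effect modification) is left to a controlled trial.

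Add a conditional safeguard. If MS-WIS severity is a predictor of MS-WIS trajectory, use either the T-1 screening score, with change measured from T0, or the growth model's latent intercept. Do not interpret the observed T0 score as a predictor of its own change. Keep T0 a separate completion from screening, as Table 3 schedules it.

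The cost is a change of wording and the choice of a covariate that is already collected. The downside is a more modest claim. The screening score also removes only part of the artefact if T-1 and T0 are completed so close together that errors are shared: at error correlation 0.6 a correlation of about -0.08 to -0.15 remains, and the larger end would just reach significance at n = 200.

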Enrolment of NHS MS Centres **Refinement of Digital READY** Ethical Approvals & Digital READY is a web-based resilience training programme for Multiple Sclerosis Governance Enrolment of health professionals (HCPs) in MS (n=50) Digital introductory workshop delivered with Psychologist Outcome Measures: Pre-READY questionnaire (Baseline Psychological Flexibility; Qualitative feedback) HCPs complete Digital READY and training (n=50, 5 HCPs per site) 2a. Digital READY participation Week 3 interval support call (delivered by Psychologist) Development of troubleshooting toolkit Outcome Measures: Psychologist notes on troubleshooting, Post-intervention questionnaire pack (Psychological flexibility, User satisfaction) and 6m follow up questionnaire (Psychological flexibility) 2b. READY training workshop (delivered by Psychologist/Project manager) Outcome Measures: Knowledge/competencies test, qualitative feedback questionnaire Sub-set: Semi-structured audio-recorded research interviews post-READY **Enrolment of PwMS** (n=250; 5 per HCP, 25 per site) Screening: Employment status, MS-WIS (Work Instability), Consent to take part Outcome Measures: Pre-READY questionnaire (Baseline Psychological Flexibility, Work Instability, other psychological factors) **PwMS complete Digital READY** Digital READY participation Week 3 interval support call (delivered by HCP) Outcome Measures: HCP notes on troubleshooting, Post-intervention and 6m follow up questionnaire packs (Psychological flexibility, Work Instability, User satisfaction, other psychological factors) Sub-set: Semi-structured audio-recorded research interviews post-intervention and 6m Analysis and write up Primary outcomes: PWMS MS-WIS at 6m, PWMS Psychological flexibility at 6m, HCP Competency/Knowledge test

Secondary outcomes: HCP Psychological flexibility at 6M

Process evaluation: Qualitative interviews, notes and questionnaire responses

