4 TRIAL DESIGN

This study is a hybrid effectiveness-implementation trial, by which we are simultaneously trialling the effectiveness of an intervention but also exploring its implementation. We will focus on 'fidelity to function', meaning that the intervention still delivers the expected outcomes, while recognising that local adaptation is vital for any intervention to work because every setting and site is different.

We will use purposive sampling for this study, which means we will actively seek to include representatives of different demographic and socio-economic backgrounds.

The trial will include the following phases:

Phase 1: Programme refinement

Findings from the recent co-production and pilot study (MS PROACTIVE) will be utilised to refine and further develop the digital READY programme. The digital programme consists of an introductory module, 6 core modules on ACT factors (Mindfulness, Acceptance, Defusion, Observer Self, Values/Meaningful action, and Future Planning) then a final booster module to be completed after a 5-week break. Aside from the booster module, it is recommended to complete one module per week and each module takes around 40 minutes to complete. There are additional exercises that participants can complete under their own initiative between modules, with accompanying guided audio-recordings (e.g. Mindfulness of the breath). A workbook accompanies the digital content, with reflective written exercises for participants to complete during and between modules. This workbook forms a personal plan that participants can refer back to on completion of the programme.

Phase 2: Getting HCPs READY

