9 DATA MANAGEMENT

9.1 Data collection tools and source document identification

This project will collect and store qualitative and quantitative data.

Participants who enter the study will be assigned a unique identifier to anonymise their records. Access to study data will be limited to those necessary for data collection, control, and analysis.

Questionnaires: Participants will complete questionnaires at baseline, week 8 and month 6. These questionnaires will include demographic data, work information, and validated scales. Data will be collected using secure GDPR-compliant online self-report forms and stored on a secure research database. The research team at participating sites will be responsible for identifying missing data and contacting the participant to complete missing data queries.

Medical record data: Data collected from medical records (e.g. MS history) will be stored securely on NHS computers and should only be shared across secure NHS email accounts or input to the research database directly by research team members involved in the study.

Qualitative data: Research interviews will be audio-recorded on an encrypted password protected dictation device. Audio files will be stored on a secure NHS computer for the duration of the study. Audio files will be sent for transcription to an approved transcription company. The transcription company must sign a confidentiality agreement before any files can be shared.

The research team at each participating site will be responsible for data collection. The CI will be responsible for the data once it is transferred to the Sponsor site.

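### Section 8.2 begins with a repeated measures ANOVA that makes no allowance for PwMS nested within HCPs and sites; if change clusters, the standard error of mean change will be too small

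*Protocol*

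**What the plan says.** The trial flow chart sets out the structure: HCPs are enrolled as "n=50, 5 HCPs per site" and PwMS as "n=250; 5 per HCP, 25 per site". Section 5 gives 10 NHS sites. In section 4 (Phase 3) the HCPs make the interval support calls to PwMS. The same section explains its focus on fidelity to function by saying that local adaptation is vital because "every setting and site is different". Objectives 3 and 4 in section 3.1 ask how context influences practitioners' support and PwMS' engagement.

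Section 8.1 starts from a modelling rule, "A minimum of 200 cases is recommended for Structural Equation Modelling (SEM) frameworks", and allows for 20% attrition, so that a "recruitment rate of at least 250 subjects should provide this minimum recommended number of cases".

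Section 8.2 starts the analysis thus: "While the first step will be to assess for any change to outcome variables over time using repeated measures ANOVA". It adds that the ANOVA gives only an overview and assumes that change is homogeneous across the study group. Latent growth curve modelling and logistic regression for predictors of trajectories follow. Neither 8.1 nor 8.2 mentions site, HCP, an ICC or a design effect.

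**The concern.** Section 3.2 expects a significant reduction in work instability among participants who complete the programme. There is no control arm, so the statistical support for that claim rests on the standard error of mean change. If some sites or HCPs produce more change than others, as objectives 3 and 4 suppose they may, two PwMS from the same site carry less information than two from different sites. A repeated measures ANOVA in its ordinary form does not see this. Its standard error is then too small and its p-value too favourable. The same holds for predictors that vary between sites or HCPs rather than between participants, and these are the context questions the study wants to answer.

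**Working it through.** **The plan's own figure.** 200 / (1 − 0.20) = 250, which matches section 8.1. The structure agrees: 10 sites × 5 HCPs = 50 HCPs; 50 × 5 = 250 PwMS; 10 × 25 = 250. The arithmetic is right for independent cases.

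**Inputs after attrition.** If the 20% loss falls evenly, 250 × 0.8 = 200 completers remain: 5 × 0.8 = 4 per HCP and 25 × 0.8 = 20 per site.

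**Assumptions (not in the protocol).** Let r_h be the correlation of change between two PwMS with the same HCP, and r_s the correlation between two PwMS at the same site with different HCPs. Three pairs are used for r_h/r_s: 0.02/0.01, 0.05/0.02 and 0.10/0.05. The test is two-sided at a nominal 5%.

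**Formulas.**
- Design effect for a mean: DE = 1 + (4 − 1)·r_h + (20 − 4)·r_s
- Effective number for the mean: 200 / DE
- Shortfall of the naive standard error: 1 − 1/√DE
- True error of a nominal 5% test: 2·(1 − Φ(1.96/√DE))

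**Results.**

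| r_h / r_s | DE | Effective n for the mean | Naive SE too small by | True error (formula) | True error (simulated) |
|---|---|---|---|---|---|
| 0.02 / 0.01 | 1 + 0.06 + 0.16 = 1.22 | 164 | 9% | 7.6% | 7.4% |
| 0.05 / 0.02 | 1 + 0.15 + 0.32 = 1.47 | 136 | 18% | 10.6% | 10.2% |
| 0.10 / 0.05 | 1 + 0.30 + 0.80 = 2.10 | 95 | 31% | 17.6% | 17.8% |

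The simulation used 10 sites × 5 HCPs × 4 PwMS, with no true mean change and a one-sample test of change. A test on the 10 site means with 9 degrees of freedom held its error at about 5% in all three cases. These figures are for a single change contrast; the omnibus test over three occasions was not simulated.

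**Which level matters.** Split the excess over 1 into a site part, 19·r_s, and an extra HCP part, 3·(r_h − r_s):
- 0.19 + 0.03 = 0.22
- 0.38 + 0.09 = 0.47
- 0.95 + 0.15 = 1.10

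Site dominates in each case. HCP clustering alone, with ICCs from 0.01 to 0.10, gives DE = 1 + 3·ICC = 1.03 to 1.30.

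**What is not affected.**
- With a site ICC of 0.05 in the level of the outcome and none in change, the simulated error of the pre-post test was 4.9%. Stable differences cancel within person.
- Regressing change on a participant-level predictor gave 4.8% to 5.7% false positives under the same three ICC pairs.
- A site-level predictor gave 7.5% to 17.9%.

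**The case against.** **Silence is not a statement of independence.** Section 8.2 names families of methods and says nothing on clustering. A separate analysis plan, not shown here, could add random effects or cluster-robust errors. That is fair, and the omission of detail alone would be weak. What remains is that 8.2 does fix a first method, and its ordinary form does not fit the structure that the flow chart plans.

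**The clustering may be small.** The programme is largely self-guided, it can be completed remotely, and the scheduled HCP contact is one call around week 3. This stands as a reason to expect little HCP clustering, and it is why the size is given only as a range. It bears less on site, where 20 completers share a setting and even an ICC of 0.01 counts.

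**Stronger readings that the documents do not support.**
- A reader might infer that the standard errors are too small as a matter of fact. Without an ICC in the protocol, this is conditional.
- A reader might infer that every predictor p-value is too optimistic. Section 8.2 names psychological flexibility and resilience, which are measured on participants, and such tests stay near nominal.
- A reader might infer that the 200 in section 8.1 is falsified. It is a case-count rule for structural equation models, with no alpha, power or effect size attached. A design effect for a mean does not convert it.
- A reader might infer from "Participants who enter the study will be assigned a unique identifier to anonymise their records" that the supporting HCP cannot be traced. A unique identifier does not exclude a link, site teams collect the data, and HCPs keep notes on their calls. The data lists in sections 7.3 and 7.4 simply do not name the supporting HCP.

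**Conclusion.** The point holds conditionally. The nesting is planned, and the protocol gives its own reasons to expect response to vary by site and practitioner. The first analysis named in section 8.2 makes no allowance for this. If change clusters to the assumed degree, the standard error of mean change is 9% to 31% too small, and a nominal 5% test errs about 7% to 18% of the time. Site is the larger source. With no clustering of change there is no error.

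The consequence is confined to the mean-change test, which 8.2 itself calls only an overview, and to predictors at site or HCP level. The correction is recommended, not a must-fix.

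**What to change.** In section 8.2, replace the repeated measures ANOVA with a mixed model for change over time. Give it site and HCP random effects on change, and small-sample degrees of freedom (for example Kenward-Roger or Satterthwaite) because there are only 10 sites. Make the same allowance wherever a site- or HCP-level predictor is tested. Ensure that site and the supporting HCP's study ID are linked to each PwMS record; the HCP link is best captured as support is given.

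In section 8.1, at most add a sentence saying that the 200 is a case-count rule with no allowance for clustering. No extra enrolment is asked.

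The cost is wording, one linking field and somewhat wider intervals. The correction is not free when the ICC is zero. For the simplest version, a test on 10 site means, the critical value is 2.26 (9 df) against 1.97 (199 df). The interval is therefore about 15% wider (2.26/1.97 = 1.15), and a test with 80% power would fall to about 70%. A mixed model with small-sample degrees of freedom will usually lose less, which is why it is preferred here.
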